7.1 Inclusion Criteria

Subject eligibility is determined according to the following criteria prior to entry into the study:

1. In the opinion of the investigator, the subject and/or parent(s) or legal guardian are capable of understanding and complying with protocol requirements.
2. The subject or the subject's parent(s) or legally acceptable representative signs and dates a written, informed consent form and any required privacy authorization prior to the initiation of any study procedures.
3. The subject has age of onset of appearance of secondary sexual characteristic earlier than age 8.0 years in girls or earlier than 9.0 years in boys and the symptom is persistent, and has confirmed diagnosis of CPP.
4. The subject has basal LH level >5.0 IU/L or peak LH >5.0 IU/L in stimulation test OR peak LH >3.3 IU/L with LH/follicle-stimulating hormone (FSH) >0.6 in stimulating test. The subject has evidence of gonadal development evaluated by ultrasonography: multiple ovarian follicles ≥ 4 mm in any ovary or uterine enlargement in females or testicular volume ≥ 4 mL in males.
5. The subject has advanced BA ≥ 1 year and BA is ≤ 11.5 years in females or ≤ 12.5 years in males OR predicted adult height <150 cm in females or < 160 cm in males OR SDS $<-2SD$ OR rapid growth defined as growth of BA /growth of chronologic age >1 . BA is determined by Greulich and Pyle standards or Tanner-Whitehouse 3 (TW3) standards at screening.
6. The subject has anticipated treatment duration of at least 2 year in investigator's judgment.
7. A male subject who is nonsterilized* and sexually active with a female partner of childbearing potential* agrees to use adequate contraception* from signing of informed consent throughout the duration of the study and for 90 days after last dose.
8. A female subject of childbearing potential* who is sexually active with a nonsterilized* male partner agrees to use routinely adequate contraception* from signing of informed consent throughout the duration of the study and for 90 days after last dose of study medication.

*Definitions and acceptable methods of contraception are defined in Section 9.1.9 Contraception and Pregnancy Avoidance Procedure and reporting responsibilities are defined in Section 9.1.10 Pregnancy.

9. The female subject who, at the discretion of the investigator, is deemed to be of child bearing potential must provide negative urine pregnancy test at test Day -1 or Day 1 prior to receiving

CONFIDENTIAL

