9.1.12 Bone Age

Bone age will be evaluated by investigators at each site using TW3 standards or Greulich-Pyle standards, and the result will be recorded in the eCRF. All BA x-ray will be sent for central reading before the end of the study. If BA x-ray result is already available – whether in the same hospital or

other hospital - within 28 days prior to first dose, the result be used for screening, under the condition that the Site retain a copy of the data/image in file notes as source documents.

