#### 6.2.2. Definition of Baseline and Change from Baseline

Baseline is defined as the last non-missing measurement prior to first dose of study drug.

The change from baseline will be calculated by subtracting the baseline values from the individual post-baseline values. If either the baseline or post-baseline value is missing, the change from baseline is set to missing as well.

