## **6.4. Efficacy Analyses**

Efficacy analyses will be summarized using the FAS analysis set. Unless otherwise specified each summary of the efficacy variables will be presented for the primary time point (Week 96) as well as each planned visit. Only observed data will be summarized, and missing data will not be imputed. However, a visit called Final Visit will also be summarized; Final Value is defined as the last treatment phase value (ie. post-baseline and  $\leq$  Week 100).

A Pre-pubertal level will be any value less than ( $<$ ) the upper limit of normal for the local laboratory, which value may be dependent on sex and/or age. If laboratory values are converted to a common unit the normal ranges should also be converted, however all comparisons to the pre-pubertal level should be performed on the original unit.

The related variables for efficacy analyses will be presented for this study.

- Tanner staging
- peak LH and FSH
- basal estradiol (female) or testosterone level (male)
- predicted adult height
- the ratio of bone age to chronological age

The number and percentage of subjects who have regression or no progression in Tanner staging at Week 96 will be summarized, individual data will be listed.

The number and percentage of subjects with suppression of peak LH and FSH, i.e. simultaneously, after stimulation to pre-pubertal level at Week 96 (Visit 10) will be summarized, individual data will be listed. For each subject at each visit the peak value (i.e. largest value of the 0, 30, 60, 90 min samples) from the stimulation tests will be used,

The number and percentage of subjects with suppression of basal estradiol level in female subjects or testosterone level in male subjects to pre-pubertal level at Week 96 (Visit 10) will be summarized, individual data will be listed.

The number and percentage of subjects with improvement in predicted adult height at Week 96 (Visit 10) compared with Baseline will be summarized, individual data will be listed.

The number and percentage of subjects with a decrease in the ratio of bone age to chronological age at Week 96 (Visit 10) compared with Baseline will be summarized, individual data will be listed. Chronological age is determined using birthdate and date of the procedure to obtain age in days and then deviding by 365.25 to obtain age in years, not truncated to an integer.

For above binary data, 95% confidence intervals will be presented with exact (Clopper-Pearson) method.

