(c) During the observational follow- up period, it is recommended to monitor the subjects who remain on treatment at least every 6 months or at a schedule based on the investigator's judgments until drug discontinuation to collect the following: height and weight, secondary sexual characteristics, hematology, clinical chemistry, ultrasonography, LH and FSH, estradiol or testosterone and ECG. ECG will also be performed 4 weeks after the last administration of leuprorelin. All subjects will be followed up annually after the last dose of leuprorelin until stable puberty is reached. At each visit, the following will be performed: Tanner staging, height and weight, BMI, menstrual history, and pelvic ultrasonography for girls. Stable puberty is defined as 2 years after menarche for girls or Tanner staging V of secondary sexual characteristics development for boys.

(d) Predicted adult height will be evaluated using Bayley-Pinneau method.

(e) Bone age will be evaluated by investigators at each site using TW3 standards or Greulich-Pyle standards at Screening. All bone age x-ray will be sent for central reading before the end of the study

(f) The female subject who, at the discretion of the investigator, is deemed to be of child bearing potential must provide negative urine pregnancy test at Day -1 or Day 1 prior to drug administration.

(g) Pelvic ultrasonography will be performed for females to measure, uterus size and number/size of follicles. For males, ultrasonography will be performed to measure the testicular volume. These results if available already can be used as part of screening. If result is already available – whether at same site or hospital – within 28 days prior to first dose, the result can be used for screening, under the condition that the Site retains a copy of the data in file notes as source documents.

(h) F test: Blood samples will be collected at 0, 30, and 60, minutes after the injection of GnRH. It is acceptable to use both GnRH and GnRHa in stimulation test; however, it is preferable to use GnRH as priority. These results if available already can be used as part of screening. If stimulation test result is already available – whether at same site or hospital – within 28 days prior to first dose, the result can be used for screening, under the condition that the Site retains a copy of the data in file notes as source documents. (i) Cranial MRI can consist of only pituitary scan, including saddle region.

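### Any rise in predicted adult height counts as improvement, and Baseline is the same screening reading that can admit the child, so reading error and selection raise the responder rate by an amount the SAP does not allow for

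*SAP*

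**What the plan says.** **Endpoint.** SAP 6.4 summarises the number and percentage of "subjects with improvement in predicted adult height at Week 96 (Visit 10) compared with Baseline". It sets no minimum rise, and the percentage gets a Clopper-Pearson 95% interval. SAP 2.2.3 lists this among the additional endpoints. The fall in the ratio of bone age to chronological age is handled in the same way.

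**Baseline.** SAP 6.2.2: "Baseline is defined as the last non-missing measurement prior to first dose of study drug". The visit lists in Protocol 9.3 and the schedule in Appendix A place PAH at Screening, Week 48 and Week 96, and bone age at Screening, Weeks 24, 48, 72 and 96. Neither is scheduled at Visit 2. Baseline for both is therefore the single screening value.

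**Entry.** Inclusion criterion 5 (Protocol 7.1) offers alternative routes:
- bone-age advance with a cap: "The subject has advanced BA ≥ 1 year and BA is ≤ 11.5 years in females" (12.5 years in males);
- low PAH: "OR predicted adult height <150 cm in females or < 160 cm in males";
- SDS below -2;
- "rapid growth defined as growth of BA /growth of chronologic age" above 1.

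**Readings.** Sites read bone age. Protocol 9.1.12 adds: "All BA x-ray will be sent for central reading before the end of the study". SAP Appendix A, note (d): "Predicted adult height will be evaluated using Bayley-Pinneau method". Neither document says whether the site or the central reading feeds the PAH and ratio analyses.

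**The concern.** Three of the four entry routes (low PAH, bone-age advance, rapid bone-age growth) favour a child whose screening film was read too old. A bone age read too high also makes PAH too low. If that same reading is Baseline, its selected error is built into the comparison, while the Week 96 error is not selected. PAH then tends to rise, and the ratio to fall, without any true change. There is no control arm to cancel this.

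The results go to the CFDA after the Week 100 visit (SAP 6.7). A reader given a percentage improved with an exact interval would naturally set it against zero. Nothing in the SAP says that about half would improve by reading error alone, or that selection adds to that half.

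**Working it through.** The plan gives no figure to reproduce: the 300 subjects have no derivation, and no SD or reliability is stated for PAH or bone age. Every numerical input below is an assumption, shown as a range.

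**Step 1. Threshold alone.** Let the observed value be the true value plus error, with errors e1 (Screening) and e2 (Week 96) independent and identically distributed. With no true change and no selection, P(e2 > e1) = 0.5. The any-rise rule therefore gives 50% before any selection.

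**Step 2. Upper bound: every child enters on low PAH.** True PAH T ~ N(μ, 6 cm), error SD s, selected if T + e1 < 150. The spurious mean gain is

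−E[e1 | selected] = s²/√(36 + s²) × φ(z)/Φ(z), with z = (150 − μ)/√(36 + s²).

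For μ = 153 and s = 3: √45 = 6.708, z = −0.447, φ/Φ = 0.361/0.327 = 1.10, so the gain is (9/6.708) × 1.10 = 1.48 cm. Simulation over μ = 150-156 and s = 2-4 gives a gain of 0.5-3.1 cm and 57%-72% improving. This is not the protocol's rule, because low PAH is only one route.

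**Step 3. The alternative routes with the cap (girls' limits).** Observed bone-age advance = A + e1, with A ~ N(m, 1 year). Observed PAH = P − k·e1, with P ~ N(μ, 6 cm). Chronological age ~ N(8, 1 year). A child is admitted if (A + e1 ≥ 1 and bone age ≤ 11.5) or observed PAH < 150. Improvement with no true change means e2 < e1, where e2 is the Week 96 bone-age reading error. Inputs: error SD 0.3, 0.5, 0.7 years; k = 3 or 5 cm per year; m = 1, 1.5, 2; μ = 150 or 156; correlation of A and P 0 or −0.5. That makes 72 combinations, one million draws each:

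| Reading-error SD (years) | Improving with no true change | Excess over 50% |
|---|---|---|
| 0.3 | 50.9%-56.0% | 0.9-6.0 points |
| 0.5 | 52.0%-59.6% | 2.0-9.6 points |
| 0.7 | 53.0%-62.7% | 3.0-12.7 points |

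Only one of the 72 combinations exceeds 62.1%, so roughly 1 to 12 points is a fair summary. The SDS and rapid-growth routes were not modelled.

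**Step 4. If the other routes were unrelated to PAH.** With test-retest reliability 0.8-0.9 and the PAH cut-off at −1 or 0 SD of the screened population, 54%-56% improve when a child has a 25% chance of qualifying by another route. The figure is 52%-53% at a 50% chance, and 50.0% when every child qualifies another way.

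**Step 5. Independent Baseline reading.** Replacing e1 by a second reading e3 that played no part in admission, with everything else as in step 3, returns 50% in every combination, within simulation error.

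**Step 6. True decline.** In step 2 with μ = 153 and s = 3, a true fall of 2 cm gives about 45% improving, and 3 cm about 36%.

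**Step 7. What the interval would show.** With 300 observed, 150/300 (50%) has a Clopper-Pearson 95% interval of 44.2%-55.8%, and 186/300 (62%) has 56.2%-67.5%. A bias of a few points could not be told from 50%. A bias at the top of the range would put the whole interval above 50% with no true change.

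**The case against.** A reader might infer that regression to the mean alone makes more than half of the children improve, or take 57%-72% as the figure for this study. The documents do not support either, for three reasons.
- The first 50% comes from the zero threshold; selection supplies only the excess.
- Criterion 5 joins its routes by OR, and a child can enter on bone-age advance whatever the PAH. The cap also keeps some over-read films out of that route, and the SDS route need not favour them.
- Protocol 4.2 suggests worsening under incomplete suppression, so zero true change over 96 weeks cannot be presumed.

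These points stand, and they limit the size of the claim. They do not remove the direction of the bias: in step 3, with the cap and the OR rule, every combination stayed above 50%.

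It can also be said that the central reading may already be intended for analysis, which would remove most of the problem. That is possible, but the SAP does not say so. Finally, the endpoint is additional, nothing is tested, and individual data are listed. That is why this is a modest point.

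**Conclusion.** The point holds in a limited form. The no-change value of the PAH responder rate is about 50%, and using the eligibility reading as Baseline pushes it up by roughly 1 to 12 points more under the assumptions of step 3. The bias would be larger if most children entered on low PAH and smaller if most entered by routes unrelated to it. The documents give neither the route mix nor the reading error, so no single figure can be fixed.

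The observed rate need not exceed 50%: a true decline could bring it lower, although the selection bias would still act upward. Nor is 50% the rate expected in untreated children; it is what the arithmetic gives when nothing changes. The bone-age ratio endpoint shares the problem in direction; its size was not computed separately.

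**What to change.** In SAP 6.4:
1. State that PAH (Bayley-Pinneau) and the bone-age to chronological-age ratio at Baseline, Week 48 and Week 96 are derived from measured height and the central bone-age reading, so that the site reading used for eligibility is never its own Baseline.
2. Report the mean PAH change with a 95% confidence interval beside the responder percentage.
3. Note that an any-rise responder rate has a no-change value of about 50%, not 0%.

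A table split at screening PAH 150/160 cm is tempting but should appear only with the central-reading Baseline. With site Baselines it creates the opposite artefact: under the step 2 inputs, only 37%-47% of children at or above 150 cm improve with no true change. Nor should the SAP declare that the no-effect value differs from 50% in the low-PAH group, because item 1 returns the reading-error part to 50%.

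The cost is SAP wording and one summary row, with no new visits or films. The central re-read removes reader error only. Error in the film itself or in the height measurement stays in Baseline, and the percentage may come out slightly less favourable.

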## **6.5. Safety Analyses**

For all safety endpoints, Baseline is defined as the last non-missing measurement prior to first dose of study drug. Safety data will be summarized using the safety analysis set.

### **6.5.1. Adverse Events**

Adverse events, including SAEs, are recorded in the eCRFs. AEs observed during the treatment period will be classified as treatment emergent adverse events (TEAEs) while those recorded during the follow-up period will be classified as clinical events. Each AE will be coded to system organ class (SOC) and preferred term (PT) using the Medical Dictionary for Regulatory Activities (MedDRA).

TEAEs are defined as AEs with onset occurring during the treatment phase and/or within 30 days (onset date – last date of dose +1≤ 30) after last study drug administration. However, for subjects that continue into the follow-up period, TEAEs will include all AEs up to the Week 100 visit. Clinical events will be any AE with onset after the Week 100 visit.

In general, AEs may be analyzed one of two ways. First method (subject count) is to report the count and percent of subjects reporting the AE. In this analysis a subject is only counted 1 time for the specific AE, and the percentage is with respect to the number of subjects in that safety set. For the treatment period the safety set is all subjects who receive at least 1 dose of study drug. For the follow-up period the safety set will be all subjects with at least 1 follow-up visit after the Week 100 visit. Second method (event count) is to count all events, for the specific AE, and calculate the rate per 100 patient years. Patient years (no. of days/365.25) for the treatment period will be determined from Day 1 to date of the Week 100 visit; patient years in follow-up period will be determined, at the subject level, from date of the Week 100 visit to date of last contact.

An SAE is defined as any untoward medical occurrence that, at any dose:

1. Results in DEATH.
2. Is LIFE THREATENING.

The term “life threatening” refers to an event in which the subject was at risk of death at the time of the event; it does not refer to an event that hypothetically might have caused death if it were more severe.
3. Requires inpatient HOSPITALIZATION or prolongation of existing hospitalization.
4. Results in persistent or significant DISABILITY/INCAPACITY.
5. Lead to a CONGENITAL ANOMALY/BIRTH DEFECT.
6. Is an IMPORTANT MEDICAL EVENT that satisfies any of the following:
  - a. May require intervention to prevent items 1 through 5 above.
  - b. May expose the subject to danger, even though the event is not immediately life threatening or fatal or does not result in hospitalization.
  - c. Includes any event or synonym described in the Takeda Medically Significant AE List (Table 6.b).

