13.1.4.1 Adverse Events

All AEs will be coded by system organ class (SOC), high level term, and preferred term (PT) using MedDRA. TEAEs are defined as AEs with onset occurring within 30 days (onset date – last date of dose +1≤ 30) after study drug administration. will be listed, and included in the summary tables. TEAEs will be summarized by treatment group by system organ class and preferred term. The following summary tables will be included in the report: summary of TEAEs and drug-related TEAEs, relationship of TEAEs to study drug (related vs. not-related), severity of TEAEs and related TEAEs. Data listings will be provided for all AEs including PTE, TEAEs, AEs leading to study drug discontinuation, and SAEs.

Incidence of polycystic ovarian syndrome in female subjects will be summarized.

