(c) During the observational follow- up period, it is recommended to monitor the subjects who remain on treatment at least every 6 months or at a schedule based on the investigator's judgments until drug discontinuation to collect the following: height and weight, secondary sexual characteristics, hematology, clinical chemistry, ultrasonography, LH and FSH, estradiol or testosterone and ECG. ECG will also be performed 4 weeks after the last administration of leuprorelin. All subjects will be followed up annually after the last dose of leuprorelin until stable puberty is reached. At each visit, the following will be performed: Tanner staging, height and weight, BMI, menstrual history, and pelvic ultrasonography for girls. Stable puberty is defined as 2 years after menarche for girls or Tanner staging V of secondary sexual characteristics development for boys.

(d) Predicted adult height will be evaluated using Bayley-Pinneau method.

(e) Bone age will be evaluated by investigators at each site using TW3 standards or Greulich-Pyle standards at Screening. All bone age x-ray will be sent for central reading before the end of the study

(f) The female subject who, at the discretion of the investigator, is deemed to be of child bearing potential must provide negative urine pregnancy test at Day -1 or Day 1 prior to drug administration.

(g) Pelvic ultrasonography will be performed for females to measure, uterus size and number/size of follicles. For males, ultrasonography will be performed to measure the testicular volume. These results if available already can be used as part of screening. If result is already available – whether at same site or hospital – within 28 days prior to first dose, the result can be used for screening, under the condition that the Site retains a copy of the data in file notes as source documents.

(h) Stimulation test: Blood samples will be collected at 0, 30, and 60, minutes after the injection of GnRH. It is acceptable to use both GnRH and GnRHa in stimulation test; however, it is preferable to use GnRH as priority. These results if available already can be used as part of screening. If stimulation test result is already available – whether at same site or hospital – within 28 days prior to first dose, the result can be used for screening, under the condition that the Site retains a copy of the data in file notes as source documents. (i) Cranial MRI can consist of only pituitary scan, including saddle region.

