### 3. STUDY DESIGN

This is a phase 4, open label study to be conducted in China, to assess long-term safety and efficacy of leuprorelin in the treatment of CPP. Approximately 300 subjects will be enrolled. The treatment duration is 96 weeks. The study will consist of 3 periods including a 4-week Screening Period, a 96-week Treatment Period and a 4-week Safety Follow-up Period. Followed by an observational follow-up period where subjects who remain on treatment will be observed at least every 24 weeks and after last dose all subjects will be followed up annually until stable puberty is reached.

- Eligible CPP subjects with body weight  $\geq 20$  kg will receive the recommended dose of leuprorelin 3.75 mg SC every 4 weeks.
- Eligible CPP subjects with body weight  $< 20$  kg will receive recommended dose of 1.88 mg SC every 4 weeks.

[figure not shown]
It is not recommended to exceed 180  $\mu\text{g}/\text{kg}$ . The dose can be adjusted based on subject's condition and investigator's judgment. Study visits, procedures, and evaluation are summarized in the Schedule of Study Procedures (Appendix A). Subjects will be followed until the end of the study, during which time they will be assessed by their treating physicians. serious adverse events (SAEs) and adverse events (AEs) will be recorded in the case report form (eCRF). Efficacy will be evaluated every 12 Weeks.

Subjects will be given the first dose of study drug in the clinic at Day 1 (Visit 2, Week 0). The last dose of study drug will be given on the day of Week 96 (Visit 10). All dosing of study drug will take place in the clinic by appropriate site staff. End of study assessment will be conducted at Week 96 (Visit 10). All subjects who receive study drug will be required to have a Final Safety Visit (Visit 11) at approximately 4 weeks after the last dose.

After the end of the study, subjects will participate in a long term observational follow-up. During the observation follow-up period, the patient visits to the referring physician are not pre-specified by the study protocol, but will follow usual clinical practice. It is anticipated that the CPP patients will visit the site for check up at least every 24 weeks. All patient-care decisions,

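### SAP 6.5.1 gives the follow-up period one AE rate and one percentage that mix time on leuprorelin with time off it, so neither estimates an on-drug or an off-drug risk

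*SAP*

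**What the plan says.** **Classification.** SAP 6.5.1 starts from dosing: "TEAEs are defined as AEs with onset occurring during the treatment phase and/or within 30 days" of the last study drug administration. It then sets a calendar limit: "However, for subjects that continue into the follow-up period, TEAEs will include all AEs up to the Week 100 visit". Later onsets get another name: "Clinical events will be any AE with onset after the Week 100 visit". Protocol 13.1.4.1 has the dose-based rule ("TEAEs are defined as AEs with onset occurring within 30 days" of dosing) and no Week 100 limit.

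**Denominators.** For the event rate, "patient years in follow-up period will be determined, at the subject level, from date of the Week 100 visit to date of last contact". For percentages, the follow-up safety set is every subject with at least one visit after Week 100. SAP 6.1 groups summaries by sex and, where applicable, by period. Neither section groups by treatment status.

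**Treatment after Week 100.** SAP section 3 describes an "observational follow-up period where subjects who remain on treatment will be observed at least every 24 weeks". Protocol Appendix A, note (c), recommends that sites "monitor the subjects who remain on treatment at least every 6 months" until the drug is stopped. Annual visits then follow the last dose until stable puberty. Inclusion criterion 6 asks for an anticipated treatment duration of at least 2 years.

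**The concern.** The Protocol justifies the study by the lack of long-term leuprorelin safety data in China. Children treated beyond Week 100 supply the longest exposure. Their events go into a group defined by calendar period, together with events in children who have stopped. A reader of the follow-up table would want the AE rate under prolonged treatment, or the rate after stopping. The planned rate and percentage answer neither question, because exposed and unexposed time share one denominator in proportions that nobody fixes or reports.

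**Working it through.** The plan states no figure for follow-up AEs, and its 300 subjects are not derived from a formula, so there is nothing to reproduce. The check sets the texts side by side and adds arithmetic that is marked as assumed where it is.

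**1. Does treatment continue across the cut?** Two years is 2 × 365.25 = 730.5 days. SAP Table 6.a puts Week 100 at Day 700. A child treated for the anticipated minimum would pass the cut still on drug. With injections every 4 weeks and the last scheduled study dose at Week 96, a next injection would fall at about Week 100.

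**2. How much on-drug time falls after the cut?** For a child treated without a break until T weeks after the Week 100 visit, the share is T / (100 + T). T is assumed:
- T = 24: 24/124 = 19%
- T = 48: 48/148 = 32%
- T = 96: 96/196 = 49%

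For scale, the treatment period gives 700/365.25 = 1.92 patient-years per child, so at most about 575 for 300 children.

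**3. What does the single rate estimate?** Let f be the on-drug share of follow-up patient-years. The reported rate is f × r_on + (1 − f) × r_off. All values below are assumptions, per 100 patient-years, with r_on = 20.

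| f | r_off = 5 | r_off = 10 | r_off = 20 |
|---|---|---|---|
| 0.10 | 6.5 | 11.0 | 20 |
| 0.25 | 8.75 | 12.5 | 20 |
| 0.50 | 12.5 | 15.0 | 20 |
| 0.75 | 16.25 | 17.5 | 20 |
| 0.90 | 18.5 | 19.0 | 20 |

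With r_off = 5 the reported rate is 6.5/20 = 33% to 18.5/20 = 93% of the on-drug rate. With r_off = 10 it is 55% to 95%. With equal rates there is no distortion. If the off-drug rate were the higher one, the direction would reverse.

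**4. Do the two SAP sentences agree for a child who stops at Week 96?** The 30-day formula (onset − last dose + 1 ≤ 30) reaches day 29 after the last dose. The Week 100 visit is nominally 700 − 672 = 28 days after it. An AE on day 29 therefore meets the 30-day rule and is also a clinical event. If Visit 11 falls 5 days early, on day 23, the overlap is days 24 to 29. The conflict is small but real.

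**5. Are the data for a split collected?** The follow-up lists in Protocol 9.3.12 contain no dosing record. The Appendix A follow-up column shows no entry for injections or concomitant medication. Section 9.3.12 also names AE assessment in its first list but not in the list for after the last dose, so off-drug events may be captured less completely. That too would affect a mixed rate.

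**The case against.** Four points on the other side have weight.

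- **The label is about period, not exposure.** A reader might infer that the SAP counts on-drug events as off-treatment. It does not say so: a clinical event is simply one from the follow-up period, and a drug relationship is not excluded. This stands.
- **The design ends study drug at Week 96.** Later leuprorelin is the treating physician's decision under usual practice. If it is not study drug, the Week 100 limit and the 30-day window nearly coincide and the label is formally consistent. If it is, the SAP departs from the Protocol's dose-based rule. The documents do not say which. This stands for the label, but the rate mixes exposed and unexposed time either way.
- **Events are not lost.** Similar tables are planned for clinical events where appropriate, SAEs and non-serious AEs are also pooled over both phases, and all AEs are listed. This stands, but none of these tables separates on-drug from off-drug time.
- **Follow-up may not happen under this plan.** Protocol 9.3.12 says that it is outside the study and undetermined, 10.2.1.1 ends routine AE collection 28 days after Visit 10, and 13.1 promises a separate SAP. Against that, Protocol 6.1 says that subjects will take part, and this SAP already sets follow-up classes and denominators. The rules should be corrected here or moved.

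**Conclusion.** The point holds for the follow-up summaries. As written, the follow-up rate and percentage mix exposed and unexposed time and estimate neither risk.

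The size is unknown. It depends on the on-drug share and on both event rates, none of which the documents give. The rates in the table show only how mixing works.

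A reader might also infer that the primary safety endpoint is compromised. The documents do not support that: TEAEs from Day 1 to the Week 100 visit are tabulated as their own period, and only the boundary overlap of a few days touches them. The consequence is confined to a descriptive summary in a single-arm study without hypothesis tests. It is worth correcting because long-term safety is the study's stated purpose, but it does not threaten the main result.

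**What to change.** 1. Keep the Day 1 to Week 100 TEAE table as the primary analysis.
2. In SAP 6.5.1, split follow-up events and person-time at the last leuprorelin dose plus the existing 30-day window. Report counts, percentages and rates separately for on-treatment and off-treatment time, with a denominator for each, and state how treatment gaps are handled. Alternatively, put these rules in the separate follow-up SAP promised in Protocol 13.1 and delete them here.
3. State whether leuprorelin given after Week 96 counts as study drug for the TEAE definition.
4. Reconcile the 30-day window with the Week 100 limit, so that no event falls under both rules.
5. Reconcile Protocol 9.3.12, 10.2.1.1 and 13.1 with Protocol 6.1 and SAP 6.5.1 on whether follow-up takes place, whether AEs are collected in it, and which SAP governs it.

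**Cost.** The wording and programming are modest. The real cost is data: the follow-up eCRF must capture the last leuprorelin dose date and any treatment gaps. The annual visits after the last dose imply that sites know that date, but the documents do not list it for collection. Nothing is gained if follow-up does not go ahead.
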